# Human breathing and possible effects on modulation of pain

As briefly mentioned, respiration and pain are co-modulated at the sub-cortical level (The PAG) as part of vital surviving functions. Human breathing is a very unique motor act. It can be controlled reflexively (automatic breathing), e.g., during sleep, while humans are also able to breathe voluntarily when needed (voluntary breathing), e.g., singing, speech, etc. Automatic breathing is believed to originate in the brainstem via the ponto-medullary respiratory oscillator. A descending bulbo-spinal projection from the oscillator synapses with the spinal cord anterior horn cells with rhythmic projections to the respiratory muscles to cause automatic breathing. The oscillator can function automatically without any peripheral feedback, and only responds to changes in pH and PCO2. (cf. review (Guz 1997)). In contrast, cortical inputs are required during voluntary breathing. Spinal motoneurons receive cortico-spinal inputs originating from discrete regions of the motor cortex where the respiratory muscles are represented. These cortical areas are clearly identified in humans (Gandevia and Rothwell 1987; Colebatch et al. 1991; Maskill et al. 1991; Sharshar et al. 2004). Clinical evidence strongly suggests that bulbo-spinal fibers project separately from the relevant corticospinal fibers. For instance, patients with brainstem lesions (Plum and Leight 1981) or very high cervical cord lesions (Davis and Plum 1972; Lahuerta et al. 1992) can breathe voluntarily, but lack automatic breathing when drowsy or asleep. Cortico-spinal pathways could bypass the brainstem respiratory centers and provide direct cortical control to the spinal respiratory motoneurons during voluntary breathing (Corfield et al. 1998). During normal functioning, spinal motoneurons are able to integrate these different sources, including descending cortico- and bulbo-spinal inputs and peripheral afferent inputs into a segmental interneuronal network (Aminoff and Sears 1971).

During voluntary breathing, humans need to voluntarily suppress autonomic control of breathing (Guz 1997; Haouzi et al. 2006) through voluntary cortical activation (the "cortical respiratory center"). Brain imaging studies (Colebatch et al. 1991; Maskill et al. 1991; Ramsay et al. 1993; Fink et al. 1995; Evans et al. 1999; Smejkal et al. 1999; Smejkal et al. 2000; Macey et al. 2003; Macey et al. 2004; Mazzone et al. 2007; Evans et al. 2009; Evans 2010) have demonstrated extensible involvements of the involvement of the control of the contro

UTHealth IRB APPROVAL DATE: 12/03/2020 The University of Texas 8

cortical areas bilaterally, including the primary motor cortex (M1), the premotor cortex, the supplementary motor area, the primary and secondary somatosensory cortices, the insula, the ACC and amygdala, and the dorsolateral prefrontal cortex. The insula is known to have strong connections to brainstem centers (Tsumori et al. 2006). Respiratory specific insular connections include the medullary respiratory chemoreceptors and pulmonary stretch receptors (Gaytan and Pasaro 1998; Hanamori et al. 1998). Activity of the insular cortex is not modulated during automatic breathing, according to breath-by-breath analysis in a recent fMRI study (Evans et al. 2009). The insula and associated operculum, however, are consistently activated during various sensorimotor respiratory tasks (Evans 2010). Change in respiratory status, e.g., urge-to-cough (Mazzone et al. 2007), needs a change in pulmonary stretch receptor or chemoreceptors (Gaytan and Pasaro 1998; Hanamori et al. 1998), leading to increased activity in the insula, thus possibly to provide respiratory interoception (Craig 2002).

the affective response to the same stimuli. Our case reports suggest that patients could tolerate the same noxious stimuli better after BreEStim. This is possibly realized by increasing pain threshold as a final result from the intervention, i.e., de-sensitization, or less sensitive to painful stimuli.

Figure 2 Change of electrical pain threshold as percentage of pre-intervention values after BreEStim and EStim in healthy subjects. Standard errors are presented (From Li et al. 2013(Li et al. 2013))

NOTE: The intensity of electrical stimulation was comparable between BreEStim and EStim, suggesting that the effect is not mainly mediated by electrical stimulation itself.

# Electrical pain threshold (% change)

The University of Texas

[figure not shown]

# IRB NUMBER: HSC-MS-20-1032 UTHealth IRB APPROVAL DATE: 12/03/2020

To test the hypothesis that BreEStim modifies pain threshold, subsequently resulting in reduction of neuropathic pain, we recently compared pain thresholds before and after BreEStim and EStim (Li et al. 2013). Two interventions were tested in the same healthy subjects in a randomized order, but at least 3 days apart in order to exclude any possible carry-over effect from the previous intervention. The results

showed that BreEStim significantly increased electrical pain threshold, while EStim significantly decreased electrical threshold. Other thresholds (thermal, electrical sensation, and tactile sensation) remained the same after both interventions. Collectively, these findings suggest that BreEStim has selectively modified electrical pain threshold, i.e., affective component.

Figure 3. Changes of electrical pain threshold as percentage of pre-intervention values after BreEStim and Breathing-only. Standard errors are shown.

To further examine whether BreEStim-induced analgesic effect is primarily caused by voluntary breathing, we compared the effect of BreEStim and Breathing-only on experimentally induced pain in healthy subjects in another study in 2015(Hu et al. 2015). The same protocol was used. Electrical pain threshold increased to a similar extent as previously reported after BreEStim, but there was almost no change after Breathing-only (Figure 3).

# BreEStim integrates multiple pain coping mechanisms

Collectively, these findings suggest that BreEStim-induced analgesia is likely caused by internal pain-coping mechanisms activated during BreEStim, rather than by EStim or Voluntary Breathing alone. It is not the purpose of this project to investigate coping mechanisms of BreEStim. Rather, according to the above literature review, we speculate that could integrate various non-pharmacological coping mechanisms into one regime for PLP management. Here are possible mechanisms for BreEStiminduced analgesia and its de-sensitization effects.

Acupuncture effect Acupuncture-related analgesic effects, via the release of endogenous opioids, are triggered when acupoints are stimulated (Hui et al. 2000; Wu et al. 2002). We want to point out that it is not the purpose of the project to distinguish whether analgesic effects are related to electroacupuncture or just electrical stimulation, since both are possibly mediated by the release of endogenous opioids when electrical stimulation is delivered transcutaneously. The main purpose of the project is to investigate whether BreEStim could be translated into management of neuropathic phantom pain in the target patient population.

Habituation to aversive stimuli Pain-related responses decrease when painful stimulation is applied repetitively. It is important to mention that habituation to aversive stimuli is not naloxonereversible, in other words, not mediated by the release of endogenous opioids (Rennefeld et al. 2010). Therefore, the above two mechanisms could have additive analgesic effects.

Influence of voluntary breathing. Effortful inspiration and expiration requires extensive cortical and subcortical activation, as mentioned above. The activation is more extensive during voluntary inspiration than voluntary expiration. The insular cortex is consistently activated during various sensorimotor respiratory tasks. Meanwhile, the insular cortex is critical in affective processing of pain. As such, unpleasantness of pain may be modulated during voluntary-breathing associated activation of the insular cortex. Furthermore, voluntary-breathing associated activation in the PAG may also enhance the ability of the PAG-RVM pathway in modulation of pain.

Anterograde amnesia to aversive stimulation When aversive stimulation is delivered during activation of the insular cortex, item-specific anterograde amnesia to the stimulation occurs (Stehberg et al. 2009). In other words, unpleasantness of peripheral noxious stimulation is not remain bared HSC-MS-20-1032

immediately after the stimulation, when the insular cortex is activated during stimulation. Expectedly, unpleasantness of peripheral painful stimulation, when triggered by voluntary inspiration (the insular cortex is activated), is decreased or not remembered. As such, it is expected to facilitate habituation to aversive stimulation even at higher intensity, subsequently increasing the analgesic effect of stimulation. A positive feedback loop could occur that patients request a higher intensity of electrical stimulation, even noxious, for a better analgesic effect.

The reward system is triggered As described above, this positive feedback loop is likely to occur by triggering the reward system, which is commonly associated with outcomes of aversive stimuli (Jensen et al. 2003). Expectedly, the intensity of aversive electrical stimulation is gradually driven higher during the course of stimulation.

#### B. Research Hypotheses and Specific Aims

The Main Research Hypothesis: In summary, BreEStim has advantages of integrating multiple internal pain-coping mechanisms to produce analgesia. We compared electrical pain threshold before and after BreEStim and EStim or Breathing-only in healthy subjects (Li et al. 2013; Li et al. 2014; Hu et al. 2015). Pain threshold was increased (i.e., de-sensitized) in both tested and contralateral hands after BreEStim, but decreased after EStim or Breathing-only without affecting other thresholds (thermal, electrical sensation, and tactile sensation). In other words, BreEStim has systemic de-sensitization effects. According to the literature, "unexplained" chronic pain after amputation, i.e., PLP, is a consequence of subsequent activation of "self-protection mechanisms" after amputationi, such as hyperamnesia and hyper-sensitization. Results from our preliminary study (Li et al. 2015) confirmed systemic sensitization in people with PLP. Therefore, we proposed the main hypothesized that BreEStim could provide nonpharmacological analgesic effects for patients with chronic phantom limb pain after limb amputation via central desensitization. Accordingly, we have the following specific aims.

Specific Aim 1: To examine whether BreEStim could have better analgesic effects on PLP It is hypothesized that BreEStim has better analgesic effect than EStim, and the analgesic effect is accompanied by elevated electrical pain thresholds. Patients with PLP will receive both BreEStim and EStim in a randomized order with at least 3 days apart. The same amount of stimulation (120 electrical stimuli) at comparable intensities will be used as in our recent studies. According to our preliminary data, we expect that BreEStim has greater pain reduction and longer lasting effect. These results will parallel with increased electrical pain thresholds after BreStim, i.e., desensitization, as compared with EStim. Specific Aim 2: To examine whether BreEStim-induced analgesic effect is dose-dependent

Similar to taking pain medications, it is hypothesized that there is a dose-response analgesic effect of BreEStim, i.e., an increased "dose" of BreEStim will have a greater impact on reduction of phantom limb pain. Two doses of BreEStim intervention (120 vs. 240 electrical stimuli) will be given to the same amputee with one week apart in a randomized order. According to our preliminary data from 3 subjects, we expect that that a high-dose BreEStim will produce a longer-lasting, but similar degree of pain reduction as compared to a low-dose BreEStim. The findings also suggest a possible cumulative effect of BreEStim, thus leading to a long term effect.

### Specific Aim 3: to examine the long-term effect of BreEStim on neuropathic PLP

It is critical to know whether patients will tolerate electrical stimulation and the induced analgesic effect will diminish or the effect will accumulate if patients receive BreEStim repetitively over time, before it is translated into a therapeutic device. It is hypothesized that the BreEStim treatment will produce a greater analgesic effect than the convention electrical stimulation (EStim) treatment in patients after traumatic amputation over a course of 2 weeks (10 consecutive workdays). We will examine the hypothesis by comparing electrical pain threshold and effectiveness in pain reduction between BreEStim and EStim in patients after traumatic amputation of one limb. The analgesic effect will be assessed by pain reduction in visual analog scale and quantitative measurement of electrical sensation and pain thresholds. The effect on general well-being and change in pain medication will be assessed.

IRB NUMBER: HSC-MS-20-1032 UTHealth IRB APPROVAL DATE: 12/03/2020

# 4. Research design and methods:

# Location: Neurorehabilitation Research Laboratory at TIRR Memorial Hermann Hospital

# C. Each sample population is appropriate and of sufficient size

# Pilot data and sample size for Experiment 1 (Aim 1)

In Experiment 1, we plan to use our recent BreEStim and EStim protocols(Li et al. 2013; Li et al. 2014) to compare the induced analgesic effects in patients after traumatic limb amputation. The same experimental protocol for quantitative sensory testing (QST) will be adopted. QST, including mechanical sensation threshold, thermal thresholds (cold/warm sensation, cold/hot pain) and electrical sensation and pain thresholds will be measured in four limbs. In the pilot study we only measured electrical sensation and pain threshold in these areas to estimate the sample size.

We have tested the protocol in 3 patients with PLP after below-the-knee amputation (BKA) (Figure 4). On average, VAS scores decreased from 5.3 to 3.2 after BreEStim. The analgesic effect lasted 16.2 hours. In contrast, VAS scores changed from 4.9 to 4.1 after EStim. The effect lasted 2.0 hours. Electrical sensation detection threshold (EDT) remained similar for both BreEStim (4.9 vs 5.0 mA, pre vs. post) and EStim (4.9 vs. 4.8 mA, pre vs. post). However, electrical pain threshold (EPT) increased from 22.8 to 29.3 mA after BreEStim – a change of 22.1%, in contrast, EPT was very similar before and after EStim (23.4 vs. 23.6 mA, pre vs. post). No difference in tactile and thermal thresholds was found.

[figure not shown]

Figure 4 BreEStim produced a better and longer lasting analgesic effect than EStim in patients with phantom limb pain.

Power analysis and estimate of sample size for Experiment 1 [name] (our biostatistician consultant) has performed power analysis based on our pilot study and historical data from the literature. A two-way repeated measures ANOVA was used to determine whether any change in VAS score was due to the interaction between INTERVENTION and TIME (i.e. whether one of two interventions is more effective at reducing VAS scores). A power analysis using the G\*power computer program (Faul et al. 2007) indicated that a sample of 12 people would be needed to detect a large effect size (> 0.8) with 85% power using a repeated measures two-way ANOVA with alpha at .05, a sample of 14 people would be needed for 90% power. To account for possible subject withdrawal (10%), we plan to recruit 16 subjects. Also to reduce the experimental bias and the order effect, the order of the interventions will be randomized.

# D. The data collection and measurement techniques are appropriate and effective

# Experimental Design

The overall research design is a within-group, randomized controlled study to compare analgesic effects between EStim and BreEStim (single-session in Exp 1, long-term intervention in Exp 3), between BreEStim120 and BreEStim240 (Exp2). We prefer this within-group comparison because 1) pain, by nature, is a subjective perception, it is difficult to control (physical, social, psychological) multi-factors between two groups; 2) It will be fair that all subjects receive the innovative intervention, which is superior to regular electrical stimulation according to our pilot data; 3) according to our recent BreEStim study in patients with spinal cord injury, the duration of analgesic effect was 15 hours after one-session of BreEStim treatment. An interval of one week for washout should be sufficient for Exp 1 & 2. The washout interval will be 2 weeks for Exp 3. It is our experience with subjects with spinal cord injury that an interval of 7 days is sufficient for subjects to return to their baseline after BreEStim treatment. (Li et al. 2016; Karri et al. 2018b; Li et al. 2018) However, we did notice that one subject with post-amputation PLP had carry-over effect for one month(Li et al. 2012a). We plan to screen these patients with longlasting carry-over effects. These patients will be excluded from the subject should this happen.

In Experiment 1, we plan to use our recent BreEStim and EStim protocols (Li et al. 2013; Li et al. 2014; Li et al. 2016) to measure mechanical sensation threshold, thermal (cold/warm detection, cold/hot pain) thresholds, and electrical sensation and pain thresholds in the treatment limb and contralateral limb. The same group of subjects will receive both BreEStim and EStim at a randomized yet balanced order with at least 7 days apart. The same amount of electrical stimulation (120 stimuli) will be given during both BreEStim and EStim. The purpose of this aim is to investigate whether BreEStim could have better analgesic effect than EStim in amputee subjects with chronic phantom limb pain as we observed in healthy subjects. We expect increased electrical pain thresholds in both limbs after BreEStim because of its central desensitization effects.

In Experiment 2, a group of subjects will receive BreEStim at two different doses (120 vs. 240 stimuli) on two different days with at least 7 days apart. The purpose is to compare the extent and duration of analysesic effects between two doses of BreEStim. We expect that BreEStim240 could have similar degree of pain reduction but with longer duration compared to BreEStim120, as shown in our pilot study. Therefore, we expect to use BreEStim240 in Experiment 3 for the long-term intervention.

[figure not shown]

Figure 7: Illustration of study design for Experiments 3

The University of Texas

IRB NUMBER: HSC-MS-20-1032 UTHealth IRB APPROVAL DATE: 12/03/2020

In Experiment 3, the same established protocol will be used (Li et al. 2012a; Li 2013). The effect of two interventions (BreEStim and EStim) will be compared. Each intervention consists of 240 stimuli/session (about 40-50 min/session), 1 session/day for 10 consecutive sessions (over 2 weeks). After a follow-up (wash-out) period of two weeks, the same subject will be treated with the other intervention with a same follow up of 2 weeks. The intensity of stimulation will be adjusted as subjects could tolerate. Electrical stimulation will be delivered to the median nerve on the dominant side. The wash-out/follow-up period of 2 weeks allows removal of accumulative or carry-over effect from the previous intervention.

It is expected that electrical pain threshold will be further increased after BreEStim with parallel reduction in pain perception, while there is no or minimum change after EStim and no significant change in pain perception. Pain threshold will be measured using QST. Pain perception will be characterized by duration and amount of change in pain on visual analog scale (VAS), i.e., how much pain is reduced and how long it lasts. As such the effect of treatment is quantified by reduction x hours.

The secondary outcome measurement will be General Well-Being (GWB) Schedule Survey and Center for Epidemiologic Studies Depression Scale (CES-D), NIMH Survey to examine the possible effect of pain reduction on general well-being, depression and quality of life of the patients. These surveys have been well validated and commonly used (Sherman et al. 1984; Wartan et al. 1997; Kooijman et al. 2000).

The long-term BreEStim treatment is expected to have some cumulative analgesic effects. However, we decide to keep the same regime of medications, because change in medications will be a confounding factor. Therefore, the subjects will be explicitly instructed to maintain the same dose and frequency of pain medications after the BreEStim treatment even if pain is improved. The collaborating investigator [name] will screen and monitor their medications. This is exploratory at this time. If the baseline pain level improves after the 2-week BreEStim treatment, a clinical trial is warranted. Change in pain medications may be explored further in the future studies.

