### 2) The proposed activities further the purposes of the Act

The intention of the Rehabilitation Act of 1973 is to promote the right of individuals with disabilities. They constitute one of the most disadvantaged groups in society, to live independently, contribute to society, pursue meaningful careers, and enjoy full inclusion and integration into all aspects of mainstream American society. It ensures that the U.S. government plays a leadership role in promoting the employment of individuals with disabilities.

The proposed project seeks to develop an alternative, noninvasive, and non-pharmacological treatment (BreEStim) for phantom limb pain management. Comparisons of analgesic effects between BreEStim and conventional electrical stimulation technique (EStim) will demonstrate superior analgesic effects by BreEStim. This has been shown in our recent preliminary study using BreEStim for neuropathic pain after spinal cord injury(Li et al. 2016; Karri et al. 2018a; Li et al. 2018). With the evidence and results to be obtained from this project, we will be able to provide strong clinical and laboratory evidence that this treatment will provide more effective and longer lasting analgesic effects for these patients, and improve general well-being of these patients. As mentioned earlier, quality of life and unemployment status is related to the severity of PLP(Whyte and Carroll 2002). Therefore, the proposed activities will obviously benefit a large population of patients, who may experience different levels of impairment and disability, by reducing their pain, emotional tension, thereby maintaining and enhancing quality of life and employment for these patients and meanwhile reducing the burden on caregivers. In this manner, the proposed activity will clearly increase these patients'

IRB NUMBER: HSC-MS-20-1032
UTHealth
IRB APPROVAL DATE: 12/03/2020
The University of Texass

2

ability to achieve the stated mandates of the Rehabilitation Act. The proposed activities, therefore, clearly further the goals of the Rehabilitation Act.

- The proposed project will have beneficial impact on the target population.

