In the EStim condition, subjects will also wear the face mask as in the BreEStim condition. The main difference is that subjects will be breathing automatically and comfortably and electrical stimulation pulses will be delivered randomly. The pulses will be programmed to randomly deliver at about every 2 seconds (between 1.9 seconds and 2.1 seconds). The pulse width will be the same at 0.1ms. Similarly, subjects control the intensity of electrical stimulation. For both BreEStim and EStim, they are strongly encouraged to increase the intensity to be painful yet tolerable gradually from their pain threshold. The level of pain with painful stimulation will be 7 on the 0-10 VAS scale. The purpose is to make the intensity of electrical stimulation comparable between two conditions. According to previous studies, the intensity is comparable between BreEStim and EStim(Li et al. 2013; Li et al. 2014). The intensity of electrical stimulation will be recorded during the course of treatment.

Two interventions (BreEStim vs. EStim) will be given to the same subject on a different day with at least 7 days apart. As in previous studies(Li et al. 2013; Li et al. 2014), a total of 120 electrical stimuli will be delivered for each intervention. The order of interventions will be randomized and balanced across subjects. Both interventions will be given at the same time of the day, as determined by subject's schedule. It is important to emphasize that subjects will be explicitly instructed to maintain the same pain regime even they feel that treatment has helped in pain reduction, such that pain reduction is mainly related to BreEStim or EStim.

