# 6. Data Collection and Analysis

Data collection details have been described above. Data analysis is described here.

**Experiment 1** Repeated-measures two-way ANOVA tests with factors INTERVENTION (2 levels, BreEStim and EStim) and TIME (pre- and post-intervention) will be tested on dependent variables, including VAS, QST thresholds (tactile, electrical, and thermal), to determine statistical significance between two interventions. Paired t-tests will be used to compare the duration of lasting hours between two interventions. p value is set at 0.05. As observed in the pilot data, we expect that BreEStim could have central desensitization and analgesic effects on patients with phantom limb pain, but no such effect after EStim. These findings would suggest that the central desensitization effect of BreEStim could be translated to analgesic effects in patients with PLP. Furthermore, the findings of analgesic effects along with desensitization effects in patients with PLP support central sensitization as a plausible mechanism that mediates post-traumatic PLP.

Experiment 2 Similar to Exp 1, repeated-measures two-way ANOVA tests with factors INTERVENTION (2 levels, BreEStim 120 vs. 240) and TIME (pre- and post-intervention) will be tested on dependent variables, including VAS, QST thresholds (tactile, electrical, and thermal), to determine statistical significance between two interventions. Paired t-tests will be used to compare the duration of analgesic effect (lasting hours) between two interventions. p value is set at 0.05. As shown in the pilot data, we expect that BreEStim could have dose-dependent effects on the duration but not the degree of analgesic effects. These results also suggest that BreEStim could have cumulative effects if patients receive interventions repeatedly over a period of time.

In Experiment 3, Repeated-measures two-way ANOVA will be performed to determine statistical significance between two interventions. Factors include INTERVENTION (BreEStim vs. EStim) and TREATMENT (Pre- and Post-intervention, and Followup). Variables are VAS and modified VAS and QST parameters, GWB, and CES-D. It is hypothesized that the effect of pain reduction is greater in BreEStim than in EStim for amputation patients, manifested by pain reduction on VAS assessment and parallel change of increased electrical pain threshold as shown by pilot data in Experiments 3. Furthermore, pain reduction is accompanied by improvement in general well-being and mood.

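### Every efficacy variable analysed in section 6 depends on a patient who can tell the interventions apart, yet the Experiment 1 pattern is read as central desensitisation with no allowance for expectation

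*Combined protocol and SAP*

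**What the plan says.** Under Experimental Design, one reason given for the within-patient design is: "It will be fair that all subjects receive the innovative intervention, which is superior to regular electrical stimulation according to our pilot data". The background section on the purposes of the Act states the result in advance: "Comparisons of analgesic effects between BreEStim and conventional electrical stimulation technique (EStim) will demonstrate superior analgesic effects by BreEStim".

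In the Experimental setup section, a BreEStim pulse is triggered by a fast, forceful inhalation. For EStim: "The main difference is that subjects will be breathing automatically and comfortably and electrical stimulation pulses will be delivered randomly". Both conditions share the face mask, 120 stimuli (Experiment 1), a 0.1 ms pulse, an interval of about 2 seconds and a target stimulation pain of 7 out of 10. Order is randomised and balanced.

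The same section lists VAS, QST and HRV as outcomes and calls HRV objective, with 5-minute recordings before and after the interventions. HRV is described under Experiment 1 only.

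Section 6 names VAS, QST thresholds and duration of relief for Experiments 1 and 2, and VAS, modified VAS, QST, GWB and CES-D for Experiment 3. HRV is not named for any experiment. On the expected Experiment 1 result, section 6 says: "These findings would suggest that the central desensitization effect of BreEStim could be translated to analgesic effects in patients with PLP".

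**The concern.** Patients perform an effortful breathing task in one condition and sit passively in the other, and each patient experiences both. If they expect the new method to work better, that expectation can lower the VAS score, lengthen the reported relief and raise the stimulus level at which they first call a pulse painful. Those movements together are the pattern of analgesia plus raised electrical pain threshold that Experiment 1 would take as support for central desensitisation.

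The comparison remains usable as a practical contrast of two procedures. What is at stake is its causal reading, and a false-positive rate that can exceed the nominal 5% if expectations differ.

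**Working it through.** **1. The plan's own figure.** The Experiment 1 power section gives 12 patients for 85% power and 14 for 90% (effect size above 0.8, alpha 0.05), and recruits 16 for 10% withdrawal. It does not state the number of groups, the number of measurements or the correlation. Assuming f = 0.4, two groups, m = 4 measurements and correlation ρ = 0.5, the interaction test has noncentrality λ = f²·n·m/(1 − ρ):
- n = 12: 0.16 × 12 × 4 / 0.5 = 15.36
- n = 14: 0.16 × 14 × 4 / 0.5 = 17.92

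These are the smallest even sample sizes reaching 85% and 90%, and 14/0.90 = 15.6, rounded up to 16. The sample size is not in dispute here. I use n = 14 below.

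**2. What each analysed variable rests on.**

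| Variable | Source of the reading | Named in section 6 |
|---|---|---|
| VAS | Patient rating, partly by telephone | Yes |
| Duration of relief; reduction × hours | Built from patient ratings over time | Yes (duration in Experiments 1 and 2, modified VAS in Experiment 3) |
| Electrical, tactile and thermal thresholds | Patient says when a stimulus is felt or becomes painful | Yes |
| GWB, CES-D | Questionnaires | Yes (Experiment 3) |
| HRV | Physiological recording | No |

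**3. Pilot difference in VAS.** The three-patient pilot for Experiment 1 reports: "VAS scores decreased from 5.3 to 3.2 after BreEStim" and "VAS scores changed from 4.9 to 4.1 after EStim".
- BreEStim: 5.3 − 3.2 = 2.1
- EStim: 4.9 − 4.1 = 0.8
- Difference: 2.1 − 0.8 = 1.3 points

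**4. Illustration of an expectation-only shift.** With two interventions and two times, the interaction test is equivalent to a paired t-test on the difference in change. If the true effect is zero, expectation shifts that difference by b points, and its SD is s, then t follows a noncentral t distribution with n − 1 = 13 degrees of freedom and noncentrality b√n/s. The two-sided 5% critical value is 2.160.

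The documents give no SD. If 1.3 points corresponded to d = 0.8, s would be 1.3/0.8 = 1.625. This is an assumption, so a range is shown. The shifts are also assumed; they equal 23%, 38% and 62% of the pilot difference (0.3/1.3, 0.5/1.3, 0.8/1.3).

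Example: b = 0.5 and s = 1.625 give noncentrality 0.5 × √14 / 1.625 = 1.15, and a rejection rate of 18.7%.

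| Assumed SD | b = 0.3 | b = 0.5 | b = 0.8 |
|---|---|---|---|
| 1.0 | 18.0% | 41.0% | 79.0% |
| 1.625 | 9.8% | 18.7% | 40.0% |
| 3.0 | 6.4% | 8.9% | 15.2% |

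With n = 16 and SD 1.625 the rates rise to 10.6%, 21.1% and 45.3%. A larger sample does not cure a shift of this kind.

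**The case against.** Several points on the other side stand.

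- **A reader might infer that every efficacy reading in the trial is subjective.** That is not so: HRV is a planned objective outcome. The gap is that it is described under Experiment 1 only and section 6 gives it no analysis.
- **A reader might infer that nothing in the design bears on expectation.** EStim is an active comparator matched on mask, stimulus count, pulse width, approximate interval and target pain level. That controls for stimulation but leaves the breathing task, and whatever patients expect of it, unmatched.
- **The predicted pattern is selective.** Electrical pain threshold should rise while tactile and thermal thresholds, including heat and cold pain, stay the same. A general reporting bias might move all of them, so this is a planned check. It is a weak one: detection thresholds need not respond to expected pain relief, no masking of the staff measuring them is described, and failing to find a change in about 14 patients is not evidence of no change.
- **A reader might infer that patients will be told BreEStim is better.** The visible text does not say so. The statements of superiority are the investigators' rationale, and the consent text was not seen, so its wording cannot be called biased or non-neutral.
- **A reader might infer that section 6 treats any difference as mechanism.** It makes the desensitisation reading for Experiment 1 only, conditional on analgesia together with changed thresholds, and in hedged terms. Even so, it never names expectation as an alternative.
- **The rates are illustrative.** The shifts and SDs are assumed, the pilot had three patients, and d = 0.8 as a paired effect is not the plan's own power model: a two-sided paired test with n = 14 would have 79% power, not 90%. The calculation shows direction and plausible scale, nothing more.

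**Conclusion.** The point holds in a limited form. Every efficacy variable named in section 6 rests on the report or judgement of a patient who can tell the interventions apart. That patients can tell is inferred from the procedures; the protocol does not state it. No assessor masking or measure of expectation is visible, superiority is presumed, and the one objective outcome has no planned analysis. The planned tests therefore cannot separate an expectation effect on VAS and electrical pain threshold from the mechanism the Experiment 1 text favours.

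Under the stated assumptions the false-positive rate could be anywhere from just above 5% to well above it. The documents do not fix where, and they do not show that an observed difference would be due to expectation. No sample-size figure changes. This is a low-cost improvement in conduct and interpretation, not a reason to reject the comparison.

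**What to change.** 1. Require one fixed, neutral script for sessions and follow-up calls, with no statement on which intervention, or which dose in Experiment 2, is expected to do better. Apply it to the consent discussion too if the consent text is not already neutral.
2. Using existing staff, have follow-up calls and post-session QST done by a team member who is not told the order. The patient's own knowledge remains, but the assessor's is removed.
3. In section 6, state that a BreEStim–EStim difference includes any expectation effect and does not by itself establish central desensitisation.
4. Add the HRV data already being collected to the variables analysed in section 6.

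A rating of expected relief from each intervention, taken before the first period, may be collected and reported descriptively. Covariate adjustment should not be relied on: with about 14 patients it would be imprecise, and a rating taken before the first period misses expectation formed by experiencing the first intervention.

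Cost: a short script, some session organisation, a few lines in section 6 and a little more analysis. The stimulation procedures, sample size and visit schedule do not change. The downside is a more cautious conclusion about mechanism.
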